#### 3.4 Indemnity

• This is not a treatment study, rather it is a study of the impact of rapid diagnostic testing for influenza, respiratory syncytial virus, and *Streptococcus pneumoniae* infection on the management of acute cardio-pulmonary admissions in the elderly, and 18-64 year olds with chronic heart and lung conditions or pneumonia / influenza type symptoms. The investigations and monitoring that form part of this study are considered part of the normal care of adults meeting the case definitions. The Investigators and Study Nurses undertaking the clinical study (i.e., who recruit and monitor the patients, or do near patient, rapid molecular and conventional diagnostic microbiological tests) either hold, or will hold (when appointed) appointments, or honorary appointments, with the University Hospitals of Leicester Trust. Thus the investigators and their staff will be indemnified by the University of Leicester Hospitals Trust.

#### 3.5 Study risks and benefits

#### Anticipated benefit for trial participants

A potential benefit to participants is the earlier diagnosis of influenza, RSV, and *S. pneumoniae* infection, with treatment tailored accordingly. This may improve the patients' quality of life by:

- 1. Reducing adverse drug events associated with broad-spectrum antibiotics (such as nausea and vomiting, and pseudomembranous colitis),
- Patients with influenza who are diagnosed rapidly may benefit from treatment with a neuraminidase inhibitor if the interval between symptom onset and diagnosis is ≤48 h. Benefits might also accrue in the elderly with influenzal pneumonia, even if treatment is administered beyond 48h, but this has not been evaluated by RCT and is a theoretical benefit, and
- 3. Participants may benefit additionally from an increased level of monitoring of their illness in comparison to the standard level of care, with subsequent earlier recognition of complications, should they occur, and early intervention.

#### Indirect benefits

- 1. Patients and staff in the hospital will benefit from improved infection control arising from rational use of single rooms and isolation cubicles.
- 2. The appropriate prescribing of neuraminidase inhibitors in the hospital may lessen viral shedding and reduce the risk of nosocomial transmission of influenza to patients and staff.

#### Risks

No specific risks due to participation in this study are anticipated since it is a surveillance, rapid diagnosis, and natural history study – with rapid diagnostic techniques being carried out in most patients in comparison to standard diagnostic testing. This is not an intervention study, i.e., we are not testing a new treatment, which

may be better or worse than standard therapy in terms of efficacy or adverse drug events. However, it is conceivable that some patients who are identified as having *S. pneumoniae* infection by the near patient rapid diagnostic test may have polymicrobial infection and that they may be disadvantaged by any early streamlining of antimicrobial therapy, should it occur. It should be noted, however, that there are specific guidelines in Leicester for the clinical management of community acquired pneumonia, and that the Investigators will not influence the antimicrobial prescribing by the medical team caring for the patient.

No procedures, including the collection of acute and convalescent blood samples for serology, will be carried out that could not be regarded as part of the normal investigation/care of the patient. Occasionally, blood collection causes pain and bruising at the site from where blood was drawn. It may also cause lightheadedness and, rarely, fainting or infection.

#### 3.6 Confidentiality and data protection

The investigator must ensure that the subject's anonymity will be maintained. On all documents and specimens that are to be removed from the investigational sites (i.e., from the University of Leicester and University Hospitals of Leicester Trust premises or storage facilities), subjects must ONLY be identified by a Trial Identification Number, their date of birth, and initials – not by their names or clinic number. The investigator should keep a separate confidential enrolment log (Appendix III), which matches identifying codes with the subjects' names and addresses and hospital numbers.

Since the study is being sponsored by the NHS National Coordinating Centre for Health Technology Assessment (NCCHTA), the Case Report Form and its contents will be retained on University of Leicester and University Hospitals of Leicester Trust premises or storage facilities.

Patient information will be stored on a password protected computer case report form/database (on an NHS computer within a secure facility). Patients' data will be aggregated into a relational database and no individual patient will be identified during health economic analyses in the University or any other analyses. Paper details (Case Report Forms/Consent) will be kept in a locked NHS facility, with only the Study Nurses, Principal Investigator, & Senior Clinical Investigators ([name]) having access to the keys/key-code. Printouts of the computer records will be stored within a secure NHS facility for a period of 15 years for future scientific scrutiny.

#### 4 STUDY DESIGN

#### 4.1 Overall design

The study is a prospective, randomised controlled trial to evaluate the impact of rapid diagnostic testing for influenza, respiratory syncytial virus and *Streptococcus pneumoniae*, on the management and outcome of acute cardio-pulmonary admissions in the elderly (age  $\geq 65$  years), and 'high-risk' individuals (have underlying chronic heart or lung disease, including asthma) who are 18-64-years of age. Or Pneumonia / influenza type symptoms.

Patients who present to Medical Admissions' Units in Leicestershire with an acute exacerbation of chronic cardio-pulmonary illness of  $\leq$ 168 hours (7 days) duration, OR an acute cardio-pulmonary illness of  $\leq$ 7 days duration (including: pneumonia; 'influenza'/influenza-like illness; 'exacerbations of chronic obstructive pulmonary disease' (COPD); bronchitis; asthma; congestive heart failure; or cardiac arrhythmia), who satisfy the study inclusion and exclusion criteria (See Sections 5.2 and 5.3), and can be recruited to the study within a 16-hour period of initial assessment by a doctor on the Medical Admissions Unit or another ward accepting acute medical admissions, will be randomised to one of three groups:

Group 1: Rapid near patient diagnostic tests (influenza and pneumococcus), Group 2: Rapid molecular tests (influenza & RSV), plus laboratory pneumococcal antigen testing, and Group 3: Traditional 'laboratory culture' (influenza, RSV, and *S. pneumoniae*)]

All tests will eventually be done on all patients who enter the study, but patients in Groups 1 and 2 will only be provided with rapid test results relating to their randomisation group.

#### On Day 1 (Day of admission to hospital)

Potential trial participants will be identified by the nursing or medical on-call staffs who provide care on the Medical Admissions Units, or the clinical team providing care on other wards that accept acute medical admissions with cardio-pulmonary conditions. The Study Nurse or Study Doctor will identify whether the patient is able to provide signed informed consent, or whether a relative or carer should be approached for signed informed assent. Signed informed Consent (by the patient) or Assent (by a relative or carer be obtained before any trial related assessments or procedures are done. Subjects will be screened for eligibility (Inclusion/Exclusion criteria check) and recruited only if all criteria are satisfied.

Demographic data and information on possible risk factors, immunisation status, relevant medical history, medications, and the nature of the acute cardio-pulmonary illness and clinical findings will then be documented. A Quality of Life assessment will be assessed by the EuroQol and a MRC Dyspnoea scale will be completed. The study nurse will document the diagnostic studies (e.g., chest radiograph, ECG, full blood count, cardiac enzymes, PaO2) that were carried out by the admitting medical team; the nature, route of administration, and timing of any antimicrobial and antiviral treatments prescribed and given to the patient; and whether the patient was admitted to a bay area of the ward, or a single room. The study nurse will collect trial specific diagnostic specimens, including a nasopharyngeal swab for near patient (influenza, Quidel) testing, molecular diagnostic testing (influenza and RSV); and routine virological culture (influenza and RSV); blood for culture (*S. pneumoniae*) and antibody tests (influenza haemagglutination inhibition); sputum for Gram stain and culture (*S. pneumoniae*); and urine for pneumococcal antigen testing (Binax NOW).

*Follow-up: Days 2, 3, 4,5,6, 7,8,9, 10, and 28:* Subjects will be reviewed on the ward, if still an in-patient and other sources of information will be consulted so that the following data can be recorded in the CRF:

*Time when diagnostic results were made available* The time (24 hr clock and date) during the patient's hospitalisation (or after death, if relevant) when the patient's nursing/medical staff were given the results of

the different microbiological tests for influenza, RSV, and *S. pneumoniae*, together with the results, will be documented

*Treatment* The nature (name, dose, frequency, and route of administration) of all antimicrobials given to all patients within 10 days of admission will be documented. Note will be made of when 'broad-spectrum' treatment is switched to 'narrow-spectrum treatment'; when intravenous antibiotics are switched to oral therapy; and when antibiotics are discontinued. The requirement for supplemental oxygen will also be documented.

*Isolation status, admission to ITU, and ventilatory support* A record will be kept of (i) the patient's isolation status during the first 7 days of admission, and whether the patient was admitted to an ITU and/or required ventilatory support (including ward-based CPAP) during the first 10 days of admission.

*Pyrexia* The time (24 hr clock and date) during the patient's first 10 days of hospitalisation (or until death, if relevant) when the patient first became apyrexial (temperature  $\leq 37.2^{\circ}$ C), and remained so for a period of >24 hours will be recorded.

*Convalescent serology* A convalescent blood sample will be collected for paired acute and convalescent serology for influenza and RSV at 10 -90days.

*Diagnostic studies* The nature and results of all diagnostic studies (e.g., chest radiograph, ECG, full blood count, cardiac enzymes, PaO2) carried out by the medical team will be recorded.

*EuroQol* The health status of all patients will be assessed by the EuroQol on days 7 and 28. Where patients have been discharged the EuroQol will be assessed by telephone interview of the patient or by postal questionnaire or by proxy (Appendix I).

*Humoral and cell-mediated immunity to the pneumococcus.* Patients whose antigen tests for the pneumococcus are positive and an equivalent number of people whose pneumococcal test is negative will be bled on one occasion only within 5 days of hospital admission, for tests of cellular and humoral immunity to the pneumococcus.

Physical Activity Questionnaire will be completed on day 2 or 3.

*Deaths* Deaths that occur within a maximum 28 days of hospitalisation will be identified by the study nurse and recorded in the CRF. [Note: the principal investigator MUST be notified by the study nurse of all deaths that occur within 28 days of admission and of the patient's study group].

*Duration of hospitalisation* The duration of hospitalisation, until discharge or death, will be obtained from the hospital activity analysis (i.e., computerised records). It will not form part of the routine monitoring of patients by the study nurse.

*Discharge diagnosis* The patient's discharge diagnosis will be obtained from the hospital activity analysis (i.e., computerised records). It will not form part of the routine monitoring of patients by the study nurse.

*Resource use after discharge* General practitioner consultations, hospital follow-up and other resource implications (e.g., prescriptions) for the period from discharge until Day 28 will be captured by a postal questionnaire (Appendix I). Patients will receive a reminder telephone call on Day 28 to return the questionnaire by post.

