#### 2. Clinical outcomes, specifically:-

- (a) Length of hospital stay until discharge: First, for all patients in Groups 1, 2, and 3. Second, for all patients with (i) influenza; (ii) RSV; and (iii) S. pneumoniae infection in Groups 1, 2, and 3.
- (b) Fever duration (during the first 10 days of hospitalisation) Time from admission (hours) until the patient first became apyrexial (temperature ≤37.2°C), and remained so for a period of at least 24 hours:

First, in all patients in Groups 1, and 2 in comparison to Group 3.

Second, in patients with *S. pneumoniae* in Groups 1, and 2, in comparison to Group 3.

(c) Supplemental oxygen dependence and CPAP dependence (during the first 10 days of hospitalisation) Times from admission (hours) until the patient required (i) no supplemental oxygen, and (ii) no CPAP, for a period of at least 24 hours: First, in all patients in Groups 1, and 2 in comparison to Group 3.

Second, in patients with *S. pneumoniae* in Groups 1, and 2, in comparison to Group 3.

(d) Admissions to Intensive Care (during the first 10 days of hospitalisation):First, the proportion of patients with S. pneumoniae infection in Groups 1, 2, and 3.

Second, to better define the burden of influenza and RSV, the proportion of all patients with (i) influenza, and (ii) RSV who require ITU support.

- (e) Ventilatory support (during the first 10 days of hospitalisation): First, the proportion of patients with *S. pneumoniae* infection in Groups 1, 2, and 3.
  Second, to better define the burden of influenza and RSV, the proportion of all patients with (i) influenza and (ii) RSV who require ventilatory support.
- (f) Deaths (within 28 days of hospitalisation): First, the proportion of patients with S. pneumoniae infection in Groups 1, 2, and 3.

Second, to better define the burden of influenza and RSV, the proportion of all patients with (i) influenza, and (ii) RSV, who die.

- 3. Quality of life, as measured by EuroQol, and quality adjusted life years generated during the 28 days after admission, will be assessed:
  - (a) In all patients in Groups 1, and 2 in comparison to Group 3.
  - (b) Second, in patients in patients with (i) influenza, (ii) RSV, and (iii) *S. pneumoniae* in Groups 1, and 2, in comparison to Group 3.
- 4. Use of isolation facilities

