#### 6.2.10 Hospital discharge (Duration of hospitalisation/discharge diagnosis)

The duration of hospitalisation (until discharge or death) and discharge diagnosis will be obtained from the hospital activity analysis (i.e., computerised records) and recorded in the CRF.

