#### 2. Length of Stay

2752 patients would enable a Minimum Clinically Significant Difference (MCSD) [between diagnostic policies] of 1 day in the mean length of stay (assuming SD=6 days) to be detected at the 5% significance level with over 80% power, assuming a 20% dropout rate and adjusting for the fact that there are 3 groups.

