#### 7.6 Statistical analysis

All analyses for both process and clinical outcomes will be based on Intention to Treat (ITT) analyses.

Impact of test result on prescribing The time to prescription of `narrow spectrum', `oral antibiotics' or `no antibiotics' between the three groups will be assessed using survival analysis techniques, whilst the use of neuraminidase inhibitors in those with influenza will be assessed using  $\chi^2$  tests, together with 95% CIs. Further analyses to allow for potential differences in patient demographics and baseline clinical characteristics between the three diagnostic test groups, and not allowed by stratification, will make use of cox proportional hazards regression modelling in the case of time to appropriate prescribing and logistic regression techniques in the case of neuraminidase inhibitors.

*Length of hospital stay* Length of hospital stay in the three diagnostic groups will initially be compared using non-parametric methods. Further analyses to allow for potential differences in patient demographics and baseline clinical characteristics between the three diagnostic test groups, and not allowed by stratification, will make use of generalised linear models in order to accommodate any skewness in the data.

*Mortality rates* Mortality rates between the three diagnostic testing groups will be compared by means of a Log-Rank Test and Kaplan-Meier survival curves. Adjustment for potential differences in patient demographics and baseline clinical characteristics between the three diagnostic test groups, and not allowed by stratification, will make use of Cox proportional hazards regression methods.

*Diagnostic accuracy* Sensitivity, specificity, positive predictive value of molecular and near patient diagnostic tests in comparison to traditional laboratory methods will be calculated together with 95% CIs. Heterogeneity in the sensitivity and specificity with respect to patient demographics and baseline clinical characteristics will be explored as secondary analyses using patient defined sub-groups.

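### Length of stay is defined to end at discharge but collected to end at discharge or death, so an early death enters the comparison as a short stay

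*Protocol*

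**What the plan says.** The endpoint is set out in the synopsis (Endpoints, item 2(a)) and repeated in section 7.5.1: "Length of hospital stay until discharge: First, for all patients in Groups 1, 2, and 3". A second comparison covers patients with influenza, RSV and S. pneumoniae separately.

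The variable collected is described in two other places. Section 4.1 (Duration of hospitalisation) states: "The duration of hospitalisation, until discharge or death, will be obtained from the hospital activity analysis". Section 6.2.10 agrees: "The duration of hospitalisation (until discharge or death) and discharge diagnosis will be obtained from the hospital activity analysis".

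Section 7.6 makes all process and clinical analyses intention to treat and says: "Length of hospital stay in the three diagnostic groups will initially be compared using non-parametric methods". Adjusted analyses then use generalised linear models to deal with skewness. The same section names survival methods for prescribing times, mortality and time to isolation, but not for length of stay. Censoring is discussed only for costs.

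Section 7.4 powers the trial on this endpoint for a difference "of 1 day in the mean length of stay (assuming SD=6 days) to be detected at the 5% significance level with over 80% power". That calculation allows for one patient in five dropping out and for the three-way comparison.

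**The concern.** For a patient who dies in hospital the two definitions part. If the stay ends only at discharge, that patient has no endpoint value. If it ends at discharge or death, the patient has a completed stay, and a death on day 2 is a two-day stay. The protocol does not censor, rank or exclude such patients, and intention to treat keeps them in. The collected variable combined with the named methods therefore places early deaths among the shortest stays.

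The protocol treats a shorter stay as benefit: its hypotheses link rapid testing to earlier discharge, better quality of life and savings. Its stated safety worry (sections 1.5, 3.5 and 10.4) is that early narrowing of antibiotics after a rapid pneumococcal result could harm patients with polymicrobial infection. If that harm took the form of early deaths, it would shorten the apparent stay in a rapid-test arm. Length of stay is one of only two clinical endpoints with a power statement.

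**Working it through.** **The plan's own figure.** Inputs from section 7.4: 2752 elderly patients, a 1-day difference, SD 6, 5% level, 20% dropout, three groups. Equal allocation is implied by the thirds in section 7.1; a two-sided test is assumed.

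- Per group: 2752 × 0.8 / 3 = 733.9.
- Standard error of a difference: √(2 × 36 / 733.9) = 0.313 day.
- Power is 82.9% at 0.05/2 (two comparisons with Group 3) and 78.8% at 0.05/3 (all pairs). The latter becomes 80.6% if dropout is taken as dividing by 1.2. A global three-group F test gives 82.3% to 92.0%, depending on the pattern of means.

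The claim of over 80% is reproduced under the usual variants and is not in dispute. It refers to mean stay.

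**Size of the artefact.** Shift in mean stay = excess mortality × (stay otherwise expected − time of death). The protocol gives no death rate for the whole trial population, only about 2.5% for pneumococcal pneumonia (section 1.5), and nothing on when deaths occur. The mortality excesses and the 3 to 7 day gap below are assumptions.

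*Excess confined to S. pneumoniae patients.* The synopsis (Sample size) expects 221 such patients among 2752 elderly.
- Per arm: 221/3 ≈ 74 of 2752/3 ≈ 917, about 8%.
- A 10-point excess in that subset is 0.10 × 0.08 = 0.8 point across the arm.
- Shift in the arm mean: 0.008 × 3 = 0.02 day to 0.008 × 7 = 0.06 day, or 2 to 6% of the 1-day target.
- Shift within the S. pneumoniae comparison: 0.10 × 3 = 0.3 day to 0.10 × 7 = 0.7 day.

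*Excess across the whole arm.*
- 3 points: 0.03 × 3 = 0.09 to 0.03 × 7 = 0.21 day.
- 5 points: 0.05 × 3 = 0.15 to 0.05 × 7 = 0.35 day.

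*What an arm-wide excess would require of the stated mechanism.* Three points of 917 is 27.5 deaths; among 74 S. pneumoniae patients that is 37 points of excess mortality. Five points is about 46 deaths, or 62 points. If antigen testing doubled the number of cases (an assumption; the synopsis expects more but gives no figure), about 19 and 31 points would still be needed.

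**Effect on a rank comparison.** Simulation with 734 per group, gamma-distributed stay (mean 9, SD 6), mean time to death 3 days, two-sided 0.05/3, no true effect on survivors' stay and 2000 repetitions per row. All values except the SD are assumed. The test was Mann-Whitney, which the protocol does not name.

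| Mortality, arm A v arm B | Shift in mean stay (B − A), days | B wins, death coded as short stay | B wins, death ranked worst |
|---|---|---|---|
| 5% v 5% | 0.01 | 0.6% | 0.5% |
| 10% v 10% | −0.01 | 1.3% | 1.0% |
| 5% v 7% | −0.14 | 3.5% | 0% |
| 10% v 13% | −0.19 | 4.6% | 0% |
| 5% v 10% | −0.31 | 11.7% | 0% |
| 10% v 15% | −0.33 | 13.8% | 0% |

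The last column shows that the false wins come from how death is coded. It is not the analysis recommended below.

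**The case against.** The strongest reply is that sections 4.1 and 6.2.10 only name the source of the dates, and that recording an end date for everyone is compatible with a discharge endpoint. The protocol never says in words that a death counts as a short stay, and the handling of deaths could be settled in a statistical analysis plan not shown here. It is true that the reading is inferred. But two definitions stand in the protocol, neither carries a rule for deaths, and the named methods take stay as a completed quantity while survival methods are named for other outcomes. That goes beyond detail left for later.

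It is also fair to say that section 7.6 names no rank test; Kaplan-Meier and log-rank are non-parametric too. A reader might infer that a rank test is fixed, and the text does not go that far. The bias arises equally in a comparison of means.

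A reader might further infer that the protocol's own safety concern would produce a spurious gain of 10 to 35% of the target difference. The documents do not support this: the concern covers S. pneumoniae patients with polymicrobial infection, and the working shows how extreme the excess in that subset would have to be.

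Nor do the documents support saying that costs are biased. Bed-days actually used, including those of patients who die, are the right input for inpatient cost.

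Finally, a mortality excess would not pass unseen: section 7.6 compares mortality by arm, section 10.4 requires every death within 28 days to be reported with its study group, and an independent committee monitors harm. This warns a reader but does not correct the length-of-stay estimate.

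**Conclusion.** The inconsistency is real and should be resolved. Followed as written, the plan gives a length-of-stay comparison that favours an arm with more early deaths. The direction assumes that patients who die do so sooner than they would have been discharged. The bias is zero when mortality and the timing of deaths are equal between arms.

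For the powered all-patient comparison the effect is small under the mechanism the protocol itself raises: 0.02 to 0.06 day for a 10-point excess in S. pneumoniae patients. It reaches 0.1 to 0.35 day only under an assumed arm-wide excess of 3 to 5 points, for which the documents give no basis. The S. pneumoniae length-of-stay comparison is more exposed, at 0.3 to 0.7 day for the same 10-point excess. The power statement is not affected.

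**What to change.** Use one definition in the synopsis (Endpoints 2(a)) and sections 4.1, 6.2.10 and 7.5.1: time from admission to discharge alive. In section 7.6, compare arms with in-hospital death as a competing event, keeping patients who die in the risk set as never discharged alive. Do this for all patients and for the S. pneumoniae subgroup. The analysis can run to day 28, the limit to which deaths are recorded.

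Keep mean bed-days including deaths as the resource-use and costing measure and report it alongside. State in section 7.4 that the power figure refers to that mean. Add that a shorter mean stay will not be read as benefit unless the live-discharge analysis agrees.

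The cost is one extra standard analysis and a second length-of-stay summary. No new data are needed, because the schedule of assessments already records the date of discharge or of death within 28 days, and the sample size does not change.
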